2.4 Participant Flow

Participants in RGF follow the consenting, Master screening, regimen assignment, regimen-specific screening, randomization to one of two active dosages or placebo treatment, and follow-up procedures and timing described in the M-SAP, including follow-up during both the placebo-controlled period (RCT) and the active treatment extension (ATE). Detailed descriptions of study procedures and timing are specified in the Master Protocol and the RGF RSA.

2.5 Regimen Allocation

Assignment of participants to RGF is the same as described in the M-SAP.

2.6 Treatment Allocation

Approximately 300 participants assigned to RGF who are determined eligible will be randomly allocated to one of two ABBV-CLS-7262 dosages or placebo. Approximately 165 will be randomized to ABBV-CLS-7262 administered QD at a dosage of 120 mg, approximately 60 participants will be randomized to ABBV-CLS-7262 administered QD at a dosage of 240 mg, and approximately 75 participants will be randomized to placebo. Treatment assignments are based on a pre-specified permuted-block randomization schedule stratified for all combinations of use vs. non-use of riluzole, edaravone, and sodium phenylbutyrate/taurursodiol (Relyvrio® or Albrioza®) at the time of screening for the Master Protocol. The first 240 participants will be assigned in a 2:1:1 allocation ratio to 120 mg ABBV-CLS-7262, 240 mg ABBV-CLS-7262, or placebo. The final approximately 60 participants will be assigned in a 3:1 allocation ratio to 120 mg ABBV-CLS-7262 or placebo by interpreting any assignments to 240 mg ABBV-CLS-7262 as an assignment to 120 mg ABBV-CLS-7262.

2.7 Treatment Administration

Details of treatment administration are described in the applicable RSA.

2.8 Allocation Concealment

Allocation concealment is the same as described in the M-SAP with the following modification for RGF. Study drug is dispensed in kits containing two types of packets of granules, type A and type B. Kits for participants randomized to the 240 mg dosage contain 120 mg of ABBV-CLS-7262 in both type A and type B packets. Kits for participants randomized to the 120 mg dosage contain 120 mg of ABBV-CLS-7262 in type A/B packets and placebo granules in type B/A packets (contents of type A vs. type B packets in the 120 mg kits is blinded here to maintain full concealment). Kits for participants randomized to placebo contain placebo granules in both type A and type B packets. Except for the designation of packets as type A vs. type B, both active and placebo packets and granules are identical in appearance.

2.9 RGF Schedule of Activities (SoA) – Placebo Controlled Period

Activity	Master Protocol Screening ¹	Regimen Specific Screening ¹	Baseline	Week 2	Week 4 ¹³	Week 8 ¹³	Week 12	Week 16 ¹³	Week 20	Week 24/ET	Follow-Up Safety Call ¹¹
	Clinic -42 to -1 Days ¹⁵	Clinic	Clinic Day	Phone Day 14 ±3	Clinic Day 28	Clinic Day 56	Phone Day 84 ±3	Clinic Day 112 ±7	Phone Day 140	Clinic Day 168 ±7	Phone 28 days ALD+3
		-41 to 0 Days ¹⁵									
Written Informed Consent ²	x	x									
Inclusion/Exclusion Review	X	X3.									
ALS & Medical History	X	'í									
Demographics	X										
Physical Examination	x										
Neurological Exam	X	Î						Î			
Vital Signs ⁴	x		x		x	x		x		x	1
Slow Vital Capacity	x		X			x		x		X	
Muscle Strength Assessment			X			х		x		X	
ALSFRS-R	x		X		X	х	х	х	X	X	
ALSAQ-40			X							X	
ROADS			X			х		х		X	

Page 12 of 36

	Master Protocol Screening	Regimen Specific Screening ¹	Baseline	Week 2	Week 4 ¹³ Clinic Day 28 ±7	Week 813 Clinic Day 56 ±7	Week 12 Phone Day 84 ±3	Week 16 ¹³ Clinic Day 112 ±7	Week 20 Phone Day 140 ±3	Week 24/ET Clinic Day 168 ±7	Follow-Up Safety Call ¹¹ Phone
Activity	Clinic	Clinic	Clinic	Phone							
	-42 to -1 Days ¹⁵	-41 to 0 Days ¹⁵	Day 0	Day 14 ±3							28 days ALD+3
CNS Bulbar Function Scale			X			x		x		х	
12-Lead ECG	х		X			х		х		X	
Clinical Safety Labs ^{5,1,0}	х		X		х	х		x		X	
Hormone Assessments 16,19		X			X			x		Х	
Menstrual Cycle Questionnaire ¹⁸			X		x	х		x		X	
Coagulation Labs (PT, PTT, INR)	X ²¹							x			
Biomarker Blood Collection ¹⁶			X			х		x		X	
Plasma/Serum for Biomarkers ¹⁶			X			x		x		x	
Biomarker Urine Collection (Master) ¹⁷			X			x		x		X	
Biomarker Urine Collection (RGF)17			X			X		X		X	
Blood Sample for PK Analysis 16					х	X		X		X	
DNA Collection7 (optional)			х								
Blood RNA Collection ¹⁶			х			х				X	
CSF Collection ²⁶			X							x	
Concomitant Medication Review	X	X	X	х	X	х	х	х	x	X	
Adverse Event Review ⁶	x	X	X	х	x	x	X	x	X	х	х
Columbia-Suicide Severity Rating Scale			х		x	x		x		X	
Install Smartphone App ¹⁴			X								
Voice Recording ⁹			X		х	X		X		X	
Uninstall Smartphone App										X	
Assignment to the Regimen	X										
Randomization within the Regimen			x								
Administer/Dispense Study Drug			X8		Х	х		х		X10	
Drug Accountability/Compliance				X	х	х	х	х	X	X	
Exit Questionnaire										X	
Vital Status Determination ¹²										X	

- 1 Master Protocol Screening procedures must be completed within 42 days to 1 day prior to the Baseline Visit. Baseline Visit cannot occur until after all Regimen-Specific eligibility criteria have been assessed and confirmed, including return of hormone assessment lab results.
- 2 During the Master Protocol Screening Visit, participants will be consented via the Platform Trial informed consent form (ICF). After a participant is assigned to a regimen, participants will be consented a second time via the regimen-specific ICF.
- 3 At the Regimen-Specific Screening Visit, participants will have regimen-specific eligibility criteria assessed.
- 4 Vital signs include weight, systolic and diastolic pressure, respiratory rate, heart rate, pulse oximetry, and temperature. Height measured at Master Protocol Screening Visit only.
- 5 Clinical safety labs include hematology (CBC with differential), complete chemistry panel, thyroid function, and urinalysis. Serum pregnancy testing will occur in women of child-bearing potential. Two additional regimen-specific safety labs will be collected, amylase and lipase.
- 6 Adverse events that occur after signing the consent form will be recorded.
- 7 The DNA sample can be collected after the Baseline Visit if a baseline sample is not obtained or the sample is not usable.
- 8 Administer first dose of investigational product only after Baseline Visit procedures are completed.
- 9 In addition to study visits outlined in the SoA, participants will be asked to complete once weekly voice recordings at home.
- 10 Drug will only be dispensed at this visit if the participant continues in the ATE.
- 11 Participants will only have a Follow-Up Safety Call at this time if they do not continue on in the ATE. Participants who continue into ATE will have a Follow-Up Safety Call 28 + 3 days after their last dose of investigational product during the ATE period.
- 12 Vital status, defined as a determination of date of death or PAV status or date last known alive, will be determined for each randomized participant at the end of the placebo-controlled portion of their follow-up (generally the Week 24 visit, as indicated). If at that time the participant is alive, his or her vital status should be determined again at the time of the last patient last visit (LPLV) of the Regimen. We may also ascertain vital status (death or date last known alive only) at later time points by using publicly available data sources as described in section 8.15 of the Master Protocol.

- 13 Visit may be conducted via phone or telemedicine with remote services instead of in-person if this is needed to protect the safety of the participant due to a pandemic, disability, or a medically necessary reason. If an in-clinic visit is conducted remotely for disability or medically necessary reason, the next scheduled in-clinic visit must occur in-person unless otherwise approved by the Medical Monitor.
- 14 One smartphone app should be installed on the participant's phone to collect the voice recordings.
- 15 Master Protocol Screening and Regimen-Specific Screening visit windows are relative to Baseline (Day 0).
- 16 Blood sample is drawn at pre-dose (within 2 hours prior to dosing in the clinic and preferably within 15 minutes prior to dosing in the clinic).
- 17 Urine biomarker sample is collected pre-dose (within 2 hours prior to dosing in the clinic and preferably within 15 minutes prior to dosing in the clinic). Collection should preferably be of the second morning urine, as a mid-stream collection if possible.
- 18 Menstrual Cycle Questionnaire to be collected only in women of childbearing potential.
- 19 Hormone Assessments include ACTH, Cortisol, Testosterone (males only), LH (males only), and Thyroid panel (TSH, free T4, T3).
- 20 CSF collection is scheduled for this Regimen during the placebo-controlled period. CSF may be collected up to one week prior to Baseline and Week 24 Visits and must be collected prior to receiving RCT or ATE study drug, respectively.
- 21 If coagulation labs are not collected during the Master Protocol Screening Visit, they can be collected during the Regimen-Specific Screening Visit.

3. General Considerations for Data Analysis

3.1 Statistical Software

Statistical analyses will be performed using SAS (SAS Institute, NC, USA), R (R Foundation for Statistical Computing, Vienna, Austria), or JAGS (Plummer, SourceForge).

3.2 Summary Statistics

Data will be summarized with respect to disposition, demographics, pre-treatment characteristics, efficacy endpoints, safety endpoints, and tolerability. Summary statistics for continuous variables will include the number of observations, the mean, median, standard deviation, inter-quartile range, and range. Summaries of continuous secondary endpoints will include empirical cumulative distribution functions (eCDF). Summaries of categorical data will include counts, denominators, and percentages.

3.3 Precision

Results will generally be reported to 3 significant figures. Percentages will generally be reported to 0.1 percentage points. P-values will generally be reported to two digits when greater than or equal to 0.095, to three digits when greater than or equal to 0.001 and less than 0.095, and as <0.001 for all smaller values.

3.4 Transformations

Data that are strictly positive, continuous, and strongly right skewed will typically be log-transformed prior to any inferential testing. Skewness greater than 3 will be used as a guide in determining which variables to transform. This R-SAP will be updated as needed prior to regimen data lock to indicate which variables warrant transformation and how they will be transformed. Original, untransformed values will be used for all summaries. Any data transformations used in the primary and interim analyses are described in the MPRDR (Appendix 1 of the M-SAP).

3.5 Multiplicity Adjustments

A single primary analysis is planned. The default criterion for significance at the final analysis is adjusted to ensure an overall one-sided type 1 error rate less than 0.025 in the absence of early stopping for futility. If the primary efficacy endpoint meets the success criteria, secondary efficacy endpoints will be tested comparing the ABBV-CLS-7262 120 mg dose versus placebo in a pre-specified order using a fixed sequence procedure with a two-sided alpha level of 0.05 for each endpoint. After the first failure to declare significance, no endpoints lower in the sequence can be significant. Nominal comparison-wise p-values will also be reported for all analyses unless otherwise specified.

3.6 Missing Data

If baseline values of a given measure are missing, the last observed pre-treatment value will be used. Missing baseline covariates will be imputed using the mean of the respective covariate. For any baseline covariate that is transformed for analysis, means will be imputed after transformation. Instances of missing baseline covariates are assumed to be rare. This R-SAP will be updated as needed prior to regimen data lock if the prevalence of missing baseline covariates warrants more careful handling.

For analyses that depend on visit-specific data, off-schedule post-baseline observations, e.g., those collected as part of an Early Termination Visit or an unscheduled visit, will be used in place of the closest missing scheduled visit that preserves the true visit sequence if the observation time is as close or closer to the missing scheduled visit than to any other post-baseline scheduled visit. Other observations will not be carried forward. For analyses that do not depend on visit-specific data, observations will be analyzed according to the actual time observed.

The planned mixed model analyses, where applied, yield estimates that are unbiased conditional on the observed values under a missing at random assumption. Secondary analyses of efficacy endpoints that accommodate missing values are described below (see Sections 6.5.5 and 6.5.6).

4. Study Endpoints and Comparisons

4.1 Efficacy Endpoints

The primary efficacy endpoint is change from baseline through Week 24 in disease severity as measured by the ALS Functional Rating Scale-Revised (ALSFRS-R) total score and survival.

Secondary efficacy endpoints include change from baseline to Week 24 in ALSFRS-R total score, change from baseline to Week 24 in respiratory function as assessed by slow vital capacity (SVC), change from baseline to Week 24 in muscle strength of upper extremities as measured isometrically using hand-held dynamometry (HHD) and grip strength, , change from baseline to Week 24 in serum neurofilament light chain protein (NfL) concentration, and change from baseline to Week 24 in activities of daily living (ADL) as assessed by the ALS Assessment Questionnaire, 40-item version (ALSAQ-40) independence in activities of daily living (ADL) domain score.

Page 15 of 36

4.2 Pharmacokinetic Endpoint

The following pharmacokinetic (PK) endpoints will be evaluated:

 Steady state concentrations of A-1684909 and any active or inactive metabolites of interest in plasma.

4.3 Exploratory Endpoints

Change from baseline to Week 24 of following exploratory endpoints will be evaluated:

- Muscle strength: HHD lower extremity percentage, HHD global percentage,
- Biofluid biomarkers of neurodegeneration, ALS disease, and the ISR pathway, including: plasma and cerebrospinal fluid (CSF) NfL, serum creatinine, urinary p75^{ECD} (normalized to urinary creatinine), CSF GDF-15, CSF FGF21
- Patient-reported outcomes: ALSAQ-40 physical mobility, eating and drinking, communications, and emotional reactions domain scores and total score, CNS-BFS total score, ROADS total score,
- ALSFRS-R: bulbar, fine motor, gross motor, fine and gross motor combined, and respiratory domain scores,
- King's ALS Clinical Staging System stage and,
- Quantitative voice characteristics: maximum phonation time, pause rate, breathy vocal
 quality, pitch instability, regulation of voicing, articulatory precision, speaking rate,
 articulation rate, and monotonicity.

Change of secondary and exploratory endpoints from baseline to other time points and average rates of change from baseline to Week 24 will also be estimated in the ECC and ERO analysis sets (see Section 6.1 Analysis sets below for definitions).

The following exploratory time-to-event endpoints will be evaluated:

Time to clinical events: first hospitalization due to a serious adverse event (SAE), first
hospitalization due to an ALS-related SAE, first use of assisted ventilation, first placement of
a feeding tube, first time reaching King's stage 4a or 4b, death or death equivalent, death
alone.

4.4 Safety Endpoints

The safety endpoints collected up to 30 days after the last dose of study drug in the RCT will be included in the safety analysis. For participants who enroll in the ATE, only safety endpoints before ATE baseline will be included. The following safety endpoints will be evaluated:

- · Treatment-emergent adverse and serious adverse events,
- Changes in laboratory values and treatment-emergent and clinically significant laboratory abnormalities,
- Changes in ECG parameters and treatment-emergent and clinically significant ECG abnormalities, and

- Changes in vital signs and treatment-emergent and clinically significant vital sign abnormalities, and
- Treatment-emergent suicidal ideation and suicidal behavior.

Reported proportions will use as their denominator all participants in the applicable Safety sample (see Section 6.1 below). Clinically significant laboratory, ECG, and vital sign abnormalities will be reported as adverse events.

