The maximum duration of the placebo-controlled treatment portion is 24 weeks. The duration of the Active Treatment Extension (ATE) period is planned for approximately 52 weeks from the first ATE visit of the final participant in Regimen F or until the primary results of the 24-week placebo-controlled period are available and a decision about further development has been made.

Follow-up Duration

At the conclusion of the 24-week placebo-controlled treatment period of the study, all participants will continue in the ATE period of the study. Any participant who stops study medication will have a 28-day follow up safety phone call and end their participation in the regimen. The duration of the ATE period is planned for approximately 52 weeks from the first ATE visit of the final participant in Regimen F.

Total Planned Trial Duration

Including the placebo-controlled treatment period and the integral ATE period, the total planned amount of time for a participant in the trial is a minimum of approximately 86 weeks. This duration assumes a 6-week screening window, 24-week placebo-controlled treatment period, a 52-week or longer ATE period, and a 4-week safety follow-up period.

SCHEDULE OF ACTIVITIES – PLACEBO CONTROLLED PERIOD

Activity (page 1 of 2)		Master Protocol Screening ¹	Regimen Specific Screening ¹	Baseline	Week	Week 4 ¹³	Week 8 ¹³	Week 12	Week 16 ¹³	Week 20	Week 24 or Early Term.	Follow-Up Safety Call ¹¹
	Master	Clinic	Clinic	Clinic	Phone	Clinic	Clinic	Phone	Clinic	Phone	Clinic	Phone
	Protocol or Regimen- Specific	-42 to -1 Days ¹⁵	-41 to 0 Days ¹⁵	Day 0	$\begin{array}{c} \text{Day} \\ 14 \pm 3 \end{array}$	Day 28 ±7	Day 56 ±7	Day 84 ±3	Day 112 ±7	Day 140 ±3	Day 168 ±7	28 days after last dose +3 days
Written Informed Consent ²	Master	X	X									
Inclusion/Exclusion Review	Master	X	X^3									
ALS & Medical History	Master	X										
Demographics	Master	X										
Physical Examination	Master	X										
Neurological Exam	Master	X										
Vital Signs ⁴	Master	X		X		Х	X		X		X	
Slow Vital Capacity	Master	X^{15}		X			X		X		X	
Muscle Strength Assessment	Master			X			X		X		X	
ALSFRS-R	Master	X		X		X	X	X	X	X	X	
ALSAQ-40	Regimen			X							X	
ROADS	Regimen			X			X		X		X	
CNS Bulbar Function Scale	Regimen			X			X		X		X	
12-Lead ECG	Regimen	X		X			X		X		X	
Clinical Safety Labs ^{5,16}	Master	Х		X		X	X		X		X	
Hormone Assessments ^{16,19}	Regimen		X			Х			X		X	
Menstrual Cycle Questionnaire 18	Regimen			X		X	X		X		X	

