12 Vital status, defined as a determination of date of death or PAV status or date last known alive, will be determined for each participant at the end of their follow-up (generally the Week 52 visit, as indicated). If at that time the participant is alive, his or her vital status should be determined again at the time of the last participant last visit (LPLV) of the regimen. We may also ascertain vital status (death or date last known alive only) at later time points by using publicly available data sources as described in section 8.15 of the Master Protocol.

13 When a participant completes the ATE Week 52 assessments, if the results of the placebo-controlled period of the trial are not available and a decision about further development has not been made, the participant will continue treatment for additional periods of approximately 12 weeks. In such a case, an Ongoing Extension Visit should be completed in the clinic every 12

HEALEY ALS Platform Trial Regimen-Specific Appendix F, ABBV-CLS-7262 Version 3.0, 07/23/2024 CONFIDENTIAL weeks $(84 \pm 7 \text{ days})$ until the results of the placebo-controlled period of the trial are available and a decision about further development has been made, or until discontinuation from the study.

14 Assessments collected during Week 24 visit in placebo-controlled phase are the same for the Baseline visit in the ATE phase 15 CSF collection is optional in the ATE. CSF may be collected up to one week prior to ATE Week 28 and ATE Week 52 Visits.

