4.4 Active Treatment Extension Eligibility

Participants who complete the 24-week placebo-controlled period will participate in the ATE unless consent is withdrawn. Participants in the 120 mg and 240 mg active treatment groups will continue to receive the same assigned dose for the ATE period. Participants in the placebo group will be assigned to active treatment with 120 mg ABBV-CLS-7262 for the ATE period. The ATE will remain blinded to dose level and original placebo-controlled treatment assignment for sites, investigators, and participants.

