6.8 Week 24 Visit or Early Termination Visit

Participants should be instructed to hold IP on the day of the study visit. Investigational product should not be taken until after study visit procedures are complete. Participants not continuing into ATE should not take IP at this visit.

This visit will take place on Day 168 ± 7 days. The following procedures will be performed for the regimen schedule:

- ALSAQ-40
- ROADS
- CNS Bulbar Function Scale
- 12-Lead ECG
- Menstrual cycle questionnaire (for women of childbearing potential)
- Collection of blood and urine samples [pre-dose]
 - Hormone safety laboratory tests
 - Collect plasma/serum for biomarker analyses
 - Collect urine for biomarker analyses
 - Collect blood RNA
 - Blood sample for PK analysis
- Lumbar puncture for CSF collection
 - Lumbar puncture may occur up to one week prior to the Week 24 visit, and should be completed prior to dispensing or administration of any ATE IP.
- Voice recording
- Uninstall smartphone app
- Dispense IP (**Drug is only dispensed at this visit if the participant is continuing in the ATE**)
- Perform IP compliance (remind of the importance of compliance, count number of unused sachets remaining in participant's supply from the previous clinic visit)
- Remind participant to bring any unused IP to the next visit (only if continuing in ATE)

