6.11.1 ATE Week 2 Telephone Visit

This visit will take place via telephone 14 ± 3 days after the Week 24 Visit of the placebocontrolled portion of the trial. The following procedures will be performed:

- Review concomitant medications
- Assess and document AEs, including Key Study Events (see section 10.3 of Master Protocol)
- Perform IP compliance (remind of the importance of compliance)
- Remind participant to bring any unused IP to the next visit

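### Read literally, the safety cut-off in SAP 4.4 drops the Week 24 scheduled safety measurements of everyone who enters the active treatment extension

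*SAP*

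**What the plan says.** SAP 4.4 has two sentences on timing. The first is general: "The safety endpoints collected up to 30 days after the last dose of study drug in the RCT will be included in the safety analysis". The second narrows it for those who continue: "For participants who enroll in the ATE, only safety endpoints before ATE baseline will be included". The R-SAP does not define ATE baseline.

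The protocol (RSA) says what it is. Footnote 14 to the ATE Schedule of Activities reads: "Assessments collected during Week 24 visit in placebo-controlled phase are the same for the Baseline visit in the ATE phase". The ATE visits are then timed from that visit; the first telephone contact, for example, falls "14 ± 3 days after the Week 24 Visit of the placebocontrolled portion of the trial" (RSA 6.11.1).

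Entry to the ATE is the default. RSA 4.4: "Participants who complete the 24-week placebo-controlled period will participate in the ATE unless consent is withdrawn". The RSA summary, under follow-up duration, goes further: "all participants will continue in the ATE period of the study".

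Week 24 is also a scheduled placebo-controlled visit. RSA 6.8 sets it at Day 168 ± 7 and lists a 12-lead ECG and "Hormone safety laboratory tests" among its procedures. The placebo-controlled schedule in SAP 2.9 adds clinical safety labs, vital signs and C-SSRS. RSA 6.8 has participants withhold drug that day until the visit procedures are done.

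**The concern.** If ATE baseline is the Week 24 visit, a rule that keeps only what comes before it discards that visit's safety measurements for entrants. Participants who do not enter keep theirs, up to 30 days after the last dose. Week 24 or early-termination values in the safety summaries would then come only from people who did not continue, a selected group.

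Week 24 is the longest exposure at which the randomized groups can still be compared. RSA 5.10 gives animal findings as the reason for the hormone and digestive-enzyme tests. RSA 1.1 describes endocrine and exocrine pancreas effects in repeat-dose animal studies, and the completed healthy-subject studies dosed for at most 14 consecutive days. The documents do not give this reason for the ECGs, and the point does not depend on them.

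SAP 4.4 also has clinically significant laboratory, ECG and vital-sign abnormalities reported as adverse events. One first detected and dated at Week 24 would fall outside the window too.

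**Working it through.** The plan states no figure here to reproduce. The check compares the cut-off with the schedule, counts visits, and then estimates how many participants are concerned.

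**1. Where the cut-off falls.** Footnote 14 of the ATE schedule equates the ATE baseline assessments with the Week 24 assessments, and the ATE visit windows count from Week 24. ATE Day 0 is therefore the Week 24 visit, and a strict reading of the cut-off stops short of it.

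**2. Scheduled post-baseline assessments kept and lost per ATE entrant** (schedule in SAP 2.9):

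| Measure | Scheduled weeks | Kept | Lost |
|---|---|---|---|
| Clinical labs, vital signs, C-SSRS | 4, 8, 16, 24 | 3 of 4 | 1 of 4 (25%) |
| 12-lead ECG | 8, 16, 24 | 2 of 3 | 1 of 3 (33%) |
| Hormones | 4, 16, 24 | 2 of 3 | 1 of 3 (33%) |

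For every measure the last one kept is Week 16 (Day 112). Scheduled measurements would end 168 − 112 = 56 days before the nominal end of the period.

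**3. How many participants.** Inputs: about 300 randomized as 165, 60 and 75 (RSA 9.1); non-mortality dropout of 2% per month and mortality of 5% over 24 weeks (SAP Appendix 1, section 3.1).

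- Months in 168 days: 168 / 30.4375 = 5.52
- Not dropped out: 0.98^5.52 = 0.894
- Also alive: 0.894 × 0.95 = 0.850
- Reaching Week 24: 300 × 0.850 ≈ 255 (about 140 on 120 mg, 51 on 240 mg, 64 on placebo)

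As a check on sensitivity, replace the monthly rate with the 13% non-mortality dropout quoted for the ATE power calculation (RSA 9.3): 0.87 × 0.95 = 0.827, or about 248 of 300. Both figures treat every completer as an ATE entrant.

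**4. Against the rest of the plan.**

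- RSA 2.2 lists the safety endpoints under the database lock that follows the last participant's Week 24 completion.
- RSA 3.2 counts the placebo-controlled period as complete only when its last visit is done.
- SAP 6.6.4 analyzes weight, which the schedule's footnote 4 lists among the vital signs, in the repeated-measures and random-slopes models. SAP 6.5.2 and 6.5.3 define these models' contrasts as 24-week change and slope to Week 24. The literal cut-off would remove the Week 24 weights of ATE entrants from both.

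These provisions assume that Week 24 data are used. The sentence in 4.4, taken literally, removes part of them.

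**The case against.** The best defense is that ATE baseline is undefined in the R-SAP and can be read as the start of ATE dosing. The pre-dose Week 24 values would then be kept. Much supports this as the intent. Week 24 sits in the placebo-controlled schedule, only those who complete that period go on, and footnote 14 looks like a device to avoid collecting the same data twice. The sentence also has a plain purpose: without it, the 30-day tail would run into ATE exposure. The SAP's revision history describes the version 3.0 change to 4.4 as a cut-off for treatment-emergent events and says nothing of dropping a visit.

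This stands as evidence of intent. It does not supply a rule. The only text that says what ATE baseline is equates it with the Week 24 assessments, and no passage overrides 4.4. The Master SAP was not available, but SAP section 1 gives the R-SAP precedence over it.

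Two limits on size also stand. Adverse events with onset before the Week 24 visit are kept on any reading, and adverse event review continues at the Week 20 call. A reader might infer that the last third of the period has no safety coverage; the documents do not support that, because the gap is confined to scheduled measurements. The participant count rests on simulation assumptions and full ATE uptake, so it illustrates scale and does not forecast it.

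**Conclusion.** The point holds as a conflict of wording with a real consequence if programmed literally. SAP 4.4 would then exclude the Week 24 labs, hormones, ECG, vital signs and C-SSRS of ATE entrants, plus abnormalities first dated at that visit. The cost is one assessment in four or one in three per entrant, with roughly 250 of 300 participants potentially affected under the stated assumptions.

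A reader might go further and infer that the sponsor has decided to discard the Week 24 safety data of nearly all completers. The documents do not support that: the schedule, the weight analysis and the revision history all point to an unintended exclusion. The sentence should still be corrected before database lock, because as written it gives a worse result than the rest of the plan intends.

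**What to change.** Replace the second timing sentence of SAP 4.4 with wording such as:

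> For ATE participants, safety data are included up to and including the Week 24/ATE baseline assessments obtained before any ATE dose, subject to the 30-day limit after the last RCT dose. Data and events with onset after the first ATE dose are excluded; for participants who enter the ATE without re-initiating study drug, those after the Week 24 visit are excluded.

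The final clause is needed because RSA 6.10 lets participants who stopped drug but remain in follow-up enter the ATE without restarting it. They have no first ATE dose, so a cut-off defined only by that dose would never apply to them. Keeping the 30-day limit prevents the new sentence from admitting data that the preceding one excludes.

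With this wording, the scheduled Week 24 assessments of entrants within the 30-day limit count: 4 of 4 for labs, vital signs and C-SSRS, and 3 of 3 for ECG and hormones. The cost is one amended provision in the R-SAP, with no new data and no change to trial conduct.
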